Patients will receive the combination of VAY736 and ibrutinib for 6 cycles. Starting with C7D1, VAY736 will be discontinued if the patient has achieved a CR per IWCLL response criteria with no evidence of disease per radiological assessment and normal blood counts at C6D15. Ibrutinib will be administered per protocol for an additional two cycles (through C8D28). If a patient has not achieved a CR per IWCLL response criteria at C6D15, VAY736 and ibrutinib will be continued for 2 additional cycles (Cycle 7 and Cycle 8). At C9D1 (± 7 days), patients will have their final disease assessment [REDACTED] of the study. All patients who have remained on study, including those who have discontinued treatment due to reasons other than disease progression, will be assessed at this time point. For patients who achieve a complete response at this assessment, investigators may consider discontinuing ibrutinib in order to follow patients for durability of response and minimize intolerance and toxicity associated with continuous ibrutinib therapy while maximizing patient quality of life.

Figure 4-1 Study design

* Combination administered for either 6 cycles or 8 cycles, ibrutinib continued through C8D28. For patients who achieve a CR at the primary endpoint (C9D1), investigators may consider discontinuing ibrutinib.

**Patients will be evaluated for the final disease assessment on C9D1 (\pm 7 days) in accordance with IWCLL guidelines.

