Patients who discontinue one of the combination drugs (ibrutinib or VAY736) prior to six cycles of treatment for reasons other than disease progression may continue the other drug until the end of treatment period (VAY736 until C6D28 or ibrutinib until C8D28). All patients regardless of study treatment duration, who have not progressed, will have a final disease assessment at C9D1 (end of treatment period).

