2.8 Analysis of other secondary objective(s)

2.8.1 Efficacy analysis

Evaluation of anti-tumor activity will be based on investigators' assessment per IWCLL criteria (see VAY736Y2102-CSP-Appendix 1 for details) as documented in the eCRF. The variables used to evaluate anti-tumor activity are CR/CRi rate, clearance of ibrutinib resistance mutations, overall response rate (ORR), and time to progression (TTP). Analyses of these variables will use the FAS, including patients from both the escalation and expansion parts. All analyses will be provided by dose level in dose escalation and by two arms in dose expansion.

Rate of CR/CRi at C9 for expansion arm A and arm B: The proportion of patients with CR or CRi assessed by investigators per IWCLL criteria (see VAY736Y2102-CSP-Appendix 1 for details) at C9 will be provided. The rate of CR/CRi at C9 is the primary endpoint for the evaluation of anti-tumor activity and will be analyzed for each expansion arm using a Bayesian modeling approach.

A minimally informative beta distribution is used as prior distribution with parameters $a=0.25$ and $b=1$. This assumes, *a priori*, that the response rate is 20%.

Posterior summaries for CR/CRi rate (posterior mean, including 90% credible intervals and the posterior probability that the true CR/CRi rate falls in the activity intervals defined below) will be provided:

Posterior probability of response rate intervals:

- [0, 20%] – clinically not meaningful
- [20%, 40%] – moderate clinical benefit
- [40%, 100%] – superior clinical benefit

In addition, exact confidence interval (90% CI) also will be provided.

To determine which response assessments occurred at C9, response assessment dates within a window of +/- 3 days of patient's Cycle 9 visit start date or end date will be considered as C9 responses.

Clearance of ibrutinib resistance mutation for expansion arm B is defined as less than 1% mutation bearing alleles (BTKC481 and/or PCL γ 2) during treatment (up to C9). The proportion of patients with negative mutation, where negative mutation is defined as having clearance of the baseline ibrutinib resistance mutation, will be provided along with corresponding 90% exact confidence interval (CI). Note that only R665, S707, A708 and L845 variants will be considered as functional PLC γ 2 mutations. Other PLC γ 2 variants will not be considered for this analysis.

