Overall response rate (ORR) is defined as the proportion of patients with best overall response (BOR) of complete response (CR), complete response with incomplete marrow recovery (CRI), or partial response (PR), as assessed by investigators per IWCLL criteria (see VAY736Y2102-CSP-Appendix 1 for details) and will be calculated based on all response evaluations. The ORR will be calculated by dose level in dose escalation and by arm in dose expansion, and overall, and will be presented along with corresponding 90% exact confidence intervals (CI). Assessments taken after the start of alternative cancer therapy will be excluded.

Time to progression (TTP) is the time from start of treatment to the date of event which is defined as the first documented progression (defined as overall disease response assessment of PD) or death due to underlying cancer. If a patient has not had an event, time to progression is censored at the date of last adequate disease assessment. Assessments taken after the start of alternative cancer therapy will be excluded.

Median TTP (in months) with corresponding 95% CI, 25th and 75th percentiles (Brookmeyer and Crowley 1982, Klein and Moeschberger 1997) and Kaplan-Meier estimated probabilities (TTP rate) with corresponding 95% CIs (Greenwood's formula, Kalbfleisch and Prentice 1980) at several time points (3, 6, 12, 18 and 24 months) will be presented. The number (%) of progressions, deaths and patients censored will also be summarized.

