5.2.2.3 Post-baseline overall disease response evaluation

The post-baseline evaluation of overall disease response is a composite of the individual responses from peripheral blood count, lymph node, spleen, liver, bone marrow and constitutional symptoms etc.

Treatment discontinuation for any reason not related to new antineoplastic therapy will be handled using the treatment policy strategy: Tumor assessment data collected after discontinuation of study treatment will be used to derive BOR.

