5.2.4 Derivation of efficacy endpoints

5.2.4.1 Best overall response

Best overall response will be calculated by patient based on all evaluations.

The best overall disease response is the best disease response recorded from the start of the treatment until PD, death, start of new therapy, withdrawal of consent or end of study, whatever comes first. Best response will be assigned according to the following order:

1. CR
2. CRi
3. PR
4. SD
5. PD
6. Unknown

In case no post-baseline assessment is available or assessments with only unknown response status are available, the category “unknown” will be assigned as best overall response.

Based on the patients’ best overall response during the study, the following rate is calculated:

Overall response rate (ORR) is the proportion of patients with best overall response of PR or better. For the calculation of the ORR, the denominator should include all patients in the targeted patient population. Additional analysis sets can be defined in the study protocol.

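### CR/CRi at C9 has no cut-off at the start of alternative cancer therapy, although ORR and TTP do, so a remission reached on another agent could count as a response on the leading efficacy endpoint

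*SAP*

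**What the plan says.** SAP 2.8.1 defines three response or progression endpoints that use disease assessments.

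- **CR/CRi at C9.** "The rate of CR/CRi at C9 is the primary endpoint for the evaluation of anti-tumor activity". The only rule for deciding which assessments qualify is timing: "response assessment dates within a window of +/- 3 days of patient's Cycle 9 visit start date or end date". The paragraph says nothing about therapy started in between.
- **ORR.** Its paragraph ends with "Assessments taken after the start of alternative cancer therapy will be excluded".
- **TTP.** Its paragraph repeats that same sentence.

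The appendix adds a cut-off for best overall response, which runs "until PD, death, start of new therapy, withdrawal of consent or end of study, whatever comes first" (SAP 5.2.4.1). Table 5-3, situation F, in SAP 5.2.4.3 covers new anti-cancer therapy for TTP. SAP 2.1.1.7 defines the start date of alternative therapy from an eCRF field and states that ibrutinib does not count. SAP 2.6.2 treats patients with no response information as non-responders and keeps them in the denominator.

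On who is assessed, Protocol 7.1.2 says: "All patients regardless of study treatment duration, who have not progressed, will have a final disease assessment at C9D1". Protocol 4.1 says that patients still on study, "including those who have discontinued treatment due to reasons other than disease progression, will be assessed at this time point".

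**The concern.** The C9 rate is meant to show whether adding VAY736 deepens the response to ibrutinib. A remission reached after the patient moved to a different anti-cancer agent cannot show that, and the SAP recognises this for ORR and TTP. Protocol 10.5.2 has no such exclusion for any endpoint. The SAP therefore added the rule to two endpoints and left out the third, and its list of changes to protocol-specified analyses does not explain the difference.

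Two things are at stake. First, any miscounted patient moves the rate in the favourable direction. Second, the endpoints can disagree on the same evaluation: a CR/CRi counts at C9 but is excluded for ORR, so a patient with no earlier qualifying response would be a responder on one endpoint and a non-responder on the other. The study is open-label and investigator-assessed. If such a patient appeared, the rule would have to be chosen with the outcome known.

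**Working it through.** **Step 1: does any other text supply the missing rule?**

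- SAP 5.2.4.1 stops at new therapy, but for best overall response only.
- SAP 5.2.2.3 says "Treatment discontinuation for any reason not related to new antineoplastic therapy will be handled using the treatment policy strategy". It sets new therapy apart, but the sentence goes on to concern the derivation of best overall response.
- SAP 5.2.4.3, situation F, concerns TTP.
- SAP 2.6.2 covers missing responses. A recorded CR after a switch is not missing.
- SAP 2.1.1.5 keeps all completed efficacy assessments whether they fall on or after treatment. It does not mention other therapy, but it leans toward inclusion.
- Protocol 7.2.1 continues tumour assessments after discontinuation until progression, death, loss to follow-up or withdrawal of consent. New therapy is not listed.
- The stop at a new therapy in Protocol 7.1.2 belongs to the TTP follow-up after C9D1.

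None of these fills the gap for CR/CRi at C9.

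**Step 2: inputs for the size.** Prior Beta(0.25, 1) and activity cut-points 20% and 40% (SAP 2.8.1); N = 20 per arm (SAP 3.1.2). The number of switchers in CR/CRi at C9 is not in the documents. It is assumed here to be 0, 1 or 2 per arm.

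**Step 3: formula.** With x responders, the posterior is Beta(0.25 + x, 21 − x), with mean (0.25 + x)/21.25. The three benefit probabilities come from its distribution function at 0.20 and 0.40; the 90% interval is equal-tailed.

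**Step 4: reproduce the SAP.** For 8/20 the mean is 8.25/21.25 = .388, the interval is (.224, .565) and the probabilities of no, moderate and superior benefit are .026, .530 and .443. This matches Table 3-2. All five rows of that table reproduce to within 0.0005.

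**Step 5: remove the miscounted responders.** Affected patients become non-responders and N stays at 20. Starting from an observed 8/20:

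| Switchers counted as CR/CRi | Correct count | Posterior mean (90% interval) | No benefit | Superior benefit |
|---|---|---|---|---|
| 0 | 8/20 | .388 (.224, .565) | .026 | .443 |
| 1 | 7/20 | .341 (.185, .515) | .073 | .274 |
| 2 | 6/20 | .294 (.147, .464) | .170 | .143 |

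Each miscounted patient adds 1/21.25 = .047 to the mean. At the low end, one such patient turns 3/20 into 4/20 and moves the probability of no benefit from .756 to .544.

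**Step 6: smaller arms.** The SAP reports that enrolment to Arm B closed and that early termination was endorsed, so an arm may have fewer than 20 patients. If N were 10 (an assumption), one patient would add 1/11.25 = .089 to the mean.

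**The case against.** The best defence is that this is silence, not an instruction. No sentence tells the analyst to count a remission reached on another therapy, the treatment-policy wording in SAP 5.2.2.3 suggests that credit for new therapy was not intended, and the programming specifications, which are not among the documents, may hold the rule. The point about intent is fair. But the exclusion is written endpoint by endpoint, so its absence from one paragraph cannot be read as a general rule, and following the SAP text as it stands gives the unwanted result.

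The affected group is also narrow, and this stands. A reader might infer from Protocol 7.1.2 that everyone who has not progressed returns at C9D1 however early both drugs were stopped. Taken as a whole, the documents do not support that. The sentence in Protocol 4.1 is limited to patients who have remained on study. Protocol 6.1.2 takes some early stoppers off study, and so does 6.3.1.3, subject to the exception in 6.1.5. The C9 window also needs a Cycle 9 visit to anchor it. Patients who stop VAY736 may stay on ibrutinib, which is not alternative therapy. A miscounted patient must switch without progression, remain on study and meet the full CR/CRi criteria, including marrow, at C9.

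A reader might also extend the point to a CR/CRi recorded after documented progression. That does not carry the same harm. Progressed patients have no planned C9D1 assessment, and where treatment continues beyond progression under Protocol 6.1.5, a later remission would have arisen on the study drugs. Whether C9 should share the progression cut-off used for best overall response is a separate, minor consistency question.

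**Conclusion.** The point holds as a gap in the stated rule. SAP 2.8.1 excludes assessments after alternative cancer therapy for ORR and TTP and gives no such rule for CR/CRi at C9, and no other section supplies one. The possible bias is in one direction only, upward.

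Its size depends on having a patient who both switched and was in CR/CRi in the C9 window; a switcher without CR/CRi changes nothing. The documents do not show that any such patient exists, so they do not support a claim that the reported rate is inflated. With one such patient in an arm of 20, the mean is 4.7 points too high, enough to move the probability of superior benefit from .274 to .443 when 8 responders are counted.

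Severity is moderate. A reader might take the SAP's use of the word primary to mean that the trial's main conclusion is exposed. It is not: the primary objective is safety and the MTD/RD, CR/CRi is a secondary endpoint, and no test, threshold or dose decision in the documents depends on its posterior.

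**What to change.** In the CR/CRi-at-C9 paragraph of SAP 2.8.1, add the sentence already used for ORR and TTP, "Assessments taken after the start of alternative cancer therapy will be excluded", with a reference to Section 2.1.1.7 for the date. Then state that patients affected are counted as non-responders and remain in the FAS denominator, in line with SAP 2.6.2. If the sponsor prefers to count a C9 remission whatever therapy came before it, the SAP should say so and explain why ORR differs.

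The cost is one sentence and one programming condition. The date is already defined from an eCRF field, so no new data are needed. Under the SAP's own introduction, the change goes in as an amendment before database lock or an addendum after it; before lock is better, so that the rule is fixed before the final outcome data are analysed. The downside is that the reported CR/CRi rate may be slightly lower.

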7.1 Study flow and visit schedule

Table 7-1 and Table 7-2 list all of the assessments and indicate with an “X”, the visits when they are performed. Unscheduled testing may be conducted as necessary to address safety concerns. All data obtained from these assessments must be supported in the patient’s source documentation. The table indicates which assessment produce data to be entered into the database (D) or remain in source documentation only (S) (Category column). No CRF will be used as a source document.

C1D1 assessments can be conducted within 3 days prior to C1D1. On treatment assessments can be conducted within 3 days prior to the planned assessment. If screening assessments are conducted within 3 days of C1D1, they do not need to be repeated for C1D1.

After C1D1, tests and/or procedures should occur on schedule whenever possible. A visit window of +/- 3 days is allowed for assessments except imaging and PK. For PK samples, with the exception of collection(s) made on Day 1 (corresponding with dosing), if PK assessment must be delayed for scheduling purposes, it is mandatory that the correct date and time of the collection are captured in the eCRF. On PK collection days, the time windows are provided in [Table 7-6](#), [Table 7-7](#), and [Table 7-8](#). In situations when dosing is delayed, PK collections should also be delayed until the subsequent dose is given. See [Section 7.2.1](#) for windows on imaging.

Table 7-1 Visit evaluation schedule for Q2W VAY736 dosing regimen

	Category	Protocol Section	Screening	Cycle 1		Cycle 2		Cycle 3		Cycle 4		Subsequent cycles		End of study treatment (EoT)	30-day Follow up	TTP	
				1	2	4	8	15	1	15	1	2	4	8	15	1	15
Day of cycle																	
Obtain Informed Consent	D	7.1.1.1	X														
Demography	D	7.1.1.2	X														
Inclusion/exclusion criteria	D	5	X														
Relevant medical history/current medical conditions	D	7.1.1.2	X														
Diagnosis and extent of cancer	D	7.1.1.2	X														
Prior antineoplastic therapy	D	7.1.1.2	X														
Antineoplastic therapies since discontinuation of study treatment	D	7.1.2														X	X
Prior/concomitant medications	D	7.1.1.2	X													Continuous	

Physical examination	S	7.2.2.1	X	X			X	X		X			X		X (Q3M after C9)			
Performance status	D	7.2.2.4	X	X				X		X			X		X (Q3M after C9)		X	
Height	D	7.2.2.3	X															
Weight	D	7.2.2.3	X	X			X	X		X			X		X (through C6 or through C8 if continuing VAY736 treatment)			

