7.2 Assessment types

7.2.1 Efficacy assessments

Efficacy will be evaluated as per the IWCLL Guidelines ([Appendix 1](#)).

Tumor assessments will be performed at screening and according to the schedule of - assessments ([Table 7-1](#) or [Table 7-2](#), as applicable based on the dosing regimen of VAY736). All screening tumor assessments should be performed as closely as possible to the start of treatment (preferably within 7 days) and never more than 28 days before the start of treatment. On-treatment radiological examinations and MRD assessments have a +/- 7 day window.

Clinical suspicion of disease progression at any time will require a disease evaluation promptly, rather than waiting for the next scheduled tumor assessment. In case of an unscheduled or delayed disease evaluation for any reason, subsequent tumor assessments should be performed according to the originally planned schedule unless a scan has been performed within 28 days.

All patients discontinuing from the study for progressive disease must have their disease progression documented.

Chest, abdomen and pelvis CT scans are required for all subjects at screening. If clinically indicated, neck CT scans should also be acquired at screening. Post baseline scans should only be performed in these anatomical regions that demonstrated disease at baseline. In case of clinical complete response, confirmation scans of chest, abdomen and pelvis are required and neck if appropriate.

CT scans should be acquired with intravenous (i.v.) contrast. If a patient is known to have a medical contraindication to CT i.v. contrast agent or develops a contraindication during the study, a CT scan without contrast should be acquired. If inguinal and/or femoral nodes are present, every effort should be made to ensure that pelvis CT scans cover both inguinal areas in their entirety.

Magnetic resonance imaging (MRI) will be allowed only in those cases when CT scans cannot be performed. Each lesion that is measured at baseline/screening must be measured by the same method throughout the study so that the comparison is consistent. For complete details, refer to [Appendix 1](#).

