* Combination administered for either 6 cycles or 8 cycles, ibrutinib continued through C8D28. For patients who achieve a CR at the primary endpoint (C9D1), investigators may consider discontinuing ibrutinib.

**Patients will be evaluated for the final disease assessment on C9D1 (\pm 7 days) in accordance with IWCLL guidelines.

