2.6.2 Handling of missing values/censoring/discontinuations

The reason for discontinuation from study will be summarized and listed, along with dates of first and last study drug treatment, duration of exposure to study drug treatment and date of discontinuation for each patient.

Other missing data will simply be noted as missing on appropriate tables/listings.

Patients with unknown or missing response and who are treated in the study but provide no information on response at the end of treatment will be treated as non-responders and will be included in the denominator when calculating CR/CRi rate or ORR.

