2. In protocol v06 Section 10.5.2: Overall response rate (ORR) is defined as best overall response (BOR) of complete response (CR) or partial response (PR), assessed by investigators per IWCLL criteria (see Appendix 1 for details). ORR for each expansion arm along with corresponding 90% exact confidence interval (CI) will be provided.
 - In SAP Section 2.8.1, based on clinical team discussion, overall response rate (ORR) is updated and now defined as the proportion of patients with an overall disease response at C9 of complete response (CR), complete response with incomplete marrow recovery (CRI), or partial response (PR), as assessed by investigators per IWCLL criteria. The rationale is to include the additional response assessment category, CRI.
3. In protocol v06 Section 10.5.4, immunogenicity analyses are discussed to study the presence and/or concentration of anti-VAY736 antibodies (Anti-Drug Antibody).
 - SAP Sections 2.2.1, 2.2.2, 2.8.4.5.1 and 2.8.4.5.2 were added and/or modified to include the standard definitions for immunogenicity analysis sets, ADA sample status and ADA patient status, so that the immunogenicity analyses can be properly defined and performed.
4. [REDACTED]
 - In SAP Section 2.9.5, based on clinical team discussion, the definition of [REDACTED] so this is additionally updated.
5. In protocol v06 Section 14.1 Appendix 1 – Guidelines for NCI CLL Working Group 2018 (IWCLL), the guidelines consist of four response categories: CR, PR, SD, and PD.

- In SAP Section 5.2, the guidelines for efficacy evaluations for CLL studies were added. This includes updating the response categories have been updated to include two additional responses: complete response with incomplete marrow recovery (CRI) and Unknown, because the 2018 IWCLL criteria guidelines specify CRI and Unknown as possible responses. The new appendix aligns with TCO standard language. It also now specifies TTP censoring rules that were not previously detailed in the SAP.
- 6. In Protocol v06, Sections 6.6.1.1, 7.2.3.1, and 10.1.5, vomiting within 8 hours of ibrutinib administration should be collected, and the time (using the 24-hour clock) of vomiting should be recorded in the adverse events eCRF.

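### The SAP's ±3-day rule for a Cycle 9 response is narrower than the protocol's C9D1 ±7-day assessment window, so a compliant late CR/CRi can go uncounted, depending on how the visit is dated

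*SAP*

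**What the plan says.** **Analysis rule.** SAP 2.8.1 decides which responses belong to C9 by taking "response assessment dates within a window of +/- 3 days" of the patient's Cycle 9 visit start date or end date. The C9 CR/CRi rate is listed among the secondary endpoints (SAP Table 1-1), but SAP 2.8.1 calls it the primary endpoint for anti-tumor activity. It is analyzed on the FAS for each expansion arm.

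**Assessment window.** Protocol 4.1 states: "At C9D1 (± 7 days), patients will have their final disease assessment". Protocol 7.2.1 adds: "On-treatment radiological examinations and MRD assessments have a +/- 7 day window". The note under SAP Figure 1-1 says "Patients will be evaluated for the final disease assessment on C9D1" and gives the same 7-day tolerance.

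**Source of a 3-day window.** Protocol 7.1 has one for ordinary visit procedures, but it leaves imaging out: "A visit window of +/- 3 days is allowed for assessments except imaging and PK".

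**Dating.** Under SAP 5.2.2.3.4 an evaluation of CR, CRi, PR, SD or Unknown is dated by the last of its required measurements. SAP 5.2.3.2 says evaluation numbers need not line up with study visits.

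**The concern.** The SAP's window is shorter than the one sites are told to work to, and it hangs on a different date: the recorded visit rather than C9D1. A site can complete the final assessment within the protocol's limits and still produce a CR/CRi that the analysis does not recognize as a C9 response. Because the rate uses the FAS, that patient stays in the denominator and drops out of the numerator.

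The late side is the exposed side, because an evaluation takes the date of its last component. A scan a week early, with blood drawn at the visit, is dated at the visit and counted. A scan a few days after the visit pulls the whole evaluation later.

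At stake is who counts as a responder on the study's lead measure of activity, in arms planned at about 20 patients.

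**Working it through.** **Inputs.** Protocol window: days −7 to +7 around C9D1 (protocol 4.1, 7.2.1). SAP rule: within 3 days of the visit start *s* or end *e*, both counted from C9D1 (SAP 2.8.1). Evaluation date: latest required component (SAP 5.2.2.3.4). Prior Beta(0.25, 1) (SAP 2.8.1) and N = 20 per arm (SAP 3.1.2).

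**Step 1: late reach of the rule.** The latest accepted day is *e* + 3. Compliant late days rejected = max(0, 7 − (*e* + 3)) = max(0, 4 − *e*).

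| Recorded visit end *e* | Latest day accepted | Compliant late days rejected | Days admitted beyond +7 |
|---|---|---|---|
| −3 | 0 | +1 to +7 | none |
| 0 | +3 | +4 to +7 | none |
| +3 | +6 | +7 | none |
| +4 | +7 | none | none |
| +5 | +8 | none | +8 |
| +7 | +10 | none | +8 to +10 |

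The end date governs the late limit. A visit that starts on C9D1 and is recorded as ending on C9D1+4 also loses no late day.

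**Step 2: early side.** An evaluation is lost as too early only if every component precedes *s* by more than 3 days.

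**Step 3: reproduce the plan's figures.** With *x* responders the posterior is Beta(0.25 + *x*, 1 + 20 − *x*), with mean (0.25 + *x*)/21.25. For *x* = 8 the mean is 8.25/21.25 = .388, the 90% credible interval is .224 to .565, and the probabilities of a rate below 20%, from 20% to 40%, and 40% or above are .026, .530 and .443. These match SAP Table 3-2, as do its other four rows.

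**Step 4: scale of one or two lost responders.** This assumes 8 true responders in an arm of 20.

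| Counted | Posterior mean (90% CrI) | P(<20%) | P(20–40%) | P(≥40%) | Exact 90% CI |
|---|---|---|---|---|---|
| 8/20 | .388 (.224, .565) | .026 | .530 | .443 | .217–.606 |
| 7/20 | .341 (.185, .515) | .073 | .653 | .274 | .177–.558 |
| 6/20 | .294 (.147, .464) | .170 | .687 | .143 | .140–.508 |

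One lost responder lowers P(≥40%) by .443 − .274 = .169.

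**The case against.** **Visit dates may absorb the gap.** SAP 2.8.1 names both a start and an end date, which suggests visits spread over several days. If the end date moves to the last C9 procedure, late responses are captured. This stands: the loss is conditional. But the documents do not say how either date is set, so membership of the endpoint depends on an undefined quantity.

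**The dating rule is not cited.** SAP 2.8.1 refers only to response assessment dates as documented by the investigator. Applying 5.2.2.3.4 is a reasonable reading but an assumption, and it is kept as one here.

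**No decision rests on a threshold.** The endpoint is descriptive. Arm B is closed to enrollment, early termination has been endorsed (SAP Section 1), and final arm sizes are not given. This limits the consequences and does not remove the conflict.

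A reader might also infer more than the documents support:

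- *That the reported rate is biased downward.* The direction depends on the recorded visit dates. A late end date admits evaluations outside the protocol window.
- *That SAP 2.6.2 turns these patients into non-responders.* Its rule, that they "will be treated as non-responders and will be included in the denominator when calculating CR/CRi rate or ORR", is for patients who give no response information at the end of treatment. A patient with a CR on C9D1+5 has given it. The denominator effect comes from the FAS.
- *That ORR is affected.* Under SAP 2.8.1 ORR "will be calculated based on all response evaluations", so the C9 window does not touch it.
- *That the narrowing was left undisclosed.* The item on the C9 rate in SAP Section 4 is cut off in the available text, so this cannot be claimed.

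**Conclusion.** The conflict between the SAP's 3-day rule and the 7-day assessment window is plain in the text and should be fixed. The loss of responders is conditional on two things: a recorded visit end more than 3 days before the evaluation date, and dating by the latest required component. With a one-day visit on C9D1, four compliant days (+4 to +7) fall outside the rule. With a visit end at C9D1+4 or later none do, and from +5 the rule exceeds the protocol's limit.

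How many patients this affects cannot be told from the documents. The 8-to-7 comparison shows how sensitive an arm of 20 is to one patient. It does not estimate what happened.

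**What to change.** In SAP 2.8.1, replace the 3-day sentence with:

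*The C9 response is the evaluation (by evaluation number) performed as the protocol's final disease assessment, with evaluation date per Section 5.2.2.3.4 within ±7 days of the scheduled C9D1 date; if more than one qualifies, the one closest to C9D1 is used.*

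Then state how the scheduled C9D1 is derived. With eight 28-day cycles and no delay it falls 8 × 28 = 224 days after C1D1; the rule for delayed cycles has to be written down. The anchor should not be the actual visit date, because a visit at C9D1+7 would then admit evaluations up to 7 + 7 = 14 days after C9D1, further than the present rule's +10.

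**Cost.** Two sentences in the SAP and a small programming change. SAP Section 1 provides the route: an amendment before database lock or an addendum after it. The downside is slightly wider timing of what counts as C9, within limits the protocol already allows.
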